5.3.1. Selection and Timing of Doses

Baricitinib:

Baricitinib should be administered at approximately the same time each day. Patients will receive the final age-based dose of baricitinib selected in the PK assessment period of Study JAHV. Based on PK modeling, this is expected to be 4 mg for patients ≥ 6 to <18 years of age and 2 mg for patients <6 years of age, in order to produce exposures similar to those in adults after 4-mg once-daily (QD) administration.

Adalimumab:

Adalimumab will be administered as a subcutaneous injection once every 2 weeks. The dose will be based on body weight: 20 mg every 2 weeks for participants weighing <30 kg, or 40 mg every 2 weeks for patients weighing ≥ 30 kg (adalimumab summary of product characteristics [SmPC]).

6. A Priori Statistical Methods

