7.2. Method of Treatment Assignment

Patients will receive the final age-based dose of baricitinib selected in the PK assessment period of Study JAHV (Section 7.2.1). Pharmacokinetic data from Study JAHV will be provided by age cohort (12 to <18 years, 9 to <12 years, 6 to <9 years, and 2 to <6 years; see [Appendix 8](#) for updated dosing based on the current data). Enrollment in Study JAHW may be restricted to patients represented in the age cohorts for which PK data are available from Study JAHV, until JAHV PK data become available for other age groups.

All patients <6 years of age will receive oral suspension. Patients ≥ 6 to <12 years of age have the option of receiving the oral suspension. Patients >12 years will be supplied tablets only.

- Baricitinib arm: At least 20 patients (MTX-IR and/or bDMARD-IR) evaluable for primary endpoint.
- Adalimumab arm: At least 4 patients evaluable for the primary endpoint.

Assignment to treatment groups will be determined by a computer-generated random sequence using an interactive web-response system (IWRS). The IWRS will be used to assign investigational product to each patient.

Site personnel will confirm that they have located the correct packages by entering a confirmation number found on the packages into the IWRS before dispensing to the patient.

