7.2.1. Selection and Timing of Doses

Baricitinib:

Baricitinib should be administered at approximately the same time each day. Patients will receive the final age-based dose of baricitinib selected in the PK assessment period of Study JAHV. Based on PBPK modeling, this is expected to be 4-mg for patients ≥ 9 to < 18 years of age and 2-mg for patients < 9 years of age, in order to produce exposures similar to those in adults after 4-mg QD administration; see [Appendix 8](#) for updated dosing based on the current data. Refer to Section [5.5](#) for additional information.

Adalimumab:

Adalimumab will be administered as a subcutaneous injection once every 2 weeks. The dose will be based on body weight: 20 mg every 2 weeks for participants weighing < 30 kg, or 40 mg every 2 weeks for patients weighing ≥ 30 kg (adalimumab SmPC).

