7.4. Dosage Modification

Baricitinib:

The baricitinib dose and formulation for an individual patient will not change during Part A of this study. During Part B, as patients age over 9 years old, they will receive baricitinib 4 mg at their next scheduled visit, and as patients age over 6 years old, they will have the option of receiving tablets instead of suspension. For patients who progress to the ≥ 18 years age group, their current dose will be maintained.

The baricitinib dose will be reduced by 50% in patients with renal impairment (defined as eGFR < 60 mL/min/1.73 m²) at baseline.

Adalimumab:

The adalimumab dose will be based on body weight (20 mg for patients weighing < 30 kg or 40 mg for patients weighing ≥ 30 kg; adalimumab SmPC). Dose modifications are NOT permitted in patients whose body weight changes from less than 30 kg to greater than 30 kg or from greater than 30 kg to less than 30 kg during Part A.

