10.3.7. Interim Analyses

Two interim analyses will be performed to potentially stop the study early due to futility when 10 and 20 baricitinib-treated patients have completed, or had the opportunity to complete, 24 weeks of treatment. At each interim analysis, the posterior probability of the treatment response rate being lower than 40% will be calculated, and the study will be stopped if this probability is greater than 75%.

The above Bayesian decision rules can be translated to correspond to the following:

- At the first interim analysis, the study will be stopped if 2 or fewer of the 10 baricitinib-treated patients are responders.
- If the study continues, at the second interim analysis, the study will be stopped if 6 or fewer of the 20 baricitinib-treated patients are responders.

A DMC will oversee the conduct of all the Phase 3 clinical studies evaluating baricitinib in patients with JIA, JIA-U, or ANA-positive uveitis. The DMC will consist of members external to Lilly. This DMC will follow the rules defined in the DMC charter, focusing on potential and identified risks for this molecule and for this class of compounds. Membership to the DMC will include, at a minimum, specialists with expertise in pediatrics, rheumatology, statistics, and other appropriate specialties. The DMC will review and evaluate planned interim analyses on an approximate semiannual basis. This DMC will be coordinated with the DMC(s) for other ongoing studies of baricitinib in other indications, and this coordination may alter the number and timing of the interim analyses.

Study sites will receive information about interim results ONLY if they need to know for the safety of their patients.

Data that the DMC will review include, but are not limited to, study discontinuation data, AEs including SAEs, clinical laboratory data, vital signs data, and growth. The DMC may recommend continuation of the study as designed, temporary suspension of enrollment, or discontinuation of a particular dose regimen or discontinuation of the entire study. The DMC may request to review efficacy data to investigate the benefit/risk relationship in the context of safety observations for ongoing patients in the study. Details of the DMC and interim safety analyses will be documented in a DMC charter and DMC analysis plan.

Additional analyses and snapshots of study data may be performed to fulfill the need for regulatory interactions or publication purposes.

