Appendix 8. Data-based Dosing Cohorts

The dose selection for baricitinib in this patient population is informed by the Phases 2 and 3 data in adults with RA, which demonstrated a positive benefit/risk profile for the 4-mg QD dose. The PK of baricitinib in pediatric patients with JIA will be investigated in Study I4V-MC-JAHV (JAHV), and the doses selected in this study will also be used in Study JAHW.

Current JAHV data on age-based cohorts

Ages 12 to <18

The PK data from the 8 pediatric patients aged 12 to <18 years support continued dosing with the 4-mg QD dose of baricitinib in patients with JIA or JIA-uveitis. These data confirmed the recommended baricitinib dose of 4 mg QD for pediatric patients with JIA or JIA-uveitis aged 12 to <18 years.

Ages 6 to <12

The PK and safety data from the 8 pediatric patients aged 9 to <12 years support continued dosing with the 4-mg QD dose of baricitinib in patients with JIA, JIA-uveitis, or ANA positive uveitis in this age group. The observed concentrations of baricitinib in the middle age group (9 to <12 years old) were consistent with:

- the anticipated efficacious exposure level in adult patients with RA receiving baricitinib 4 mg QD,
- model-predicted mean concentrations in pediatric patients aged 9 to <12 years with JIA receiving baricitinib 4 mg QD.

The population of patients recruited at global investigative sites did not include any patients 6 to <9 years of age. The PBPK prediction suggested that a dose of 2 mg QD is likely to produce exposure in this age group more aligned with the mean adult exposure.

Next Steps for Study JAHW

An updated summary of dosing for Study JAHW is provided in the table below.

Lilly has initiated the following for Study JAHV to confirm dosing:

- Lilly has enrolled the cohort aged 6 to <9 years in the PK cohort in JAHV to receive a dose of 2 mg baricitinib in order to conduct a safety/PK analysis and to confirm the dose for this age group.
- Once the PK analysis is completed in the patients aged 6 to <9 years in JAHV, the PBPK model will be updated accordingly for the patients aged 2 to <6 years (the youngest age cohort) to verify the appropriate starting dose for the safety/PK evaluation. These patients will proceed into the Open-Label Lead-In period after the safety/PK assessment.

Updated Study JAHW Dosing Summary

Age Group	Baricitinib Dose
12 to <18 years old	4 mg
9 to <12 years old	4 mg

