6 to <9 years old	2 mg (based on predicted data – to be confirmed with observed data)
2 to <6 years old	2 mg ^a

Abbreviations: OLLI = open-label lead-in; PK = pharmacokinetic; QD = once daily.

^a To be confirmed after evaluating data from patients aged 6 to <9 years.

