5.3. Method of Assignment to Treatment

Patients will receive the final age-based dose of baricitinib selected in the pharmacokinetic (PK) assessment period of Study JAHV (Section 5.3.1). Pharmacokinetic data from Study JAHV will be provided by age cohort (12 to <18 years, 6 to <12 years, and 2 to <6 years). Enrollment in Study JAHW may be restricted to patients represented in the age cohorts for which PK data are available from Study JAHV, until JAHV PK data become available for other age groups.

All patients <6 years of age will receive oral suspension. Patients ≥ 6 to <12 years of age have the option of receiving the oral suspension. Patients ≥ 12 years will be supplied tablets only.

- **Baricitinib arm:** at least 20 patients (MTX IR and/or bDMARD IR) evaluable for the primary endpoint.
- **Adalimumab arm:** at least 4 patients evaluable for the primary endpoint.

Assignment to treatment groups will be determined by a computer-generated random sequence using an interactive web-response system (IWRS). The IWRS will be used to assign investigational product to each patient.

Site personnel will confirm that they have located the correct packages by entering a confirmation number found on the packages into the IWRS before dispensing to the patient.

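### The SAP and protocol give different ages for the expected baricitinib dose change (6 against 9), the SAP omits the protocol's age-group summaries, and its suspension compliance formula has no term for a Part B dose change

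*SAP*

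**What the plan says.** **Dose and age.** SAP 5.3.1 expects 4 mg from age 6 and "2 mg for patients <6 years of age, in order to produce exposures similar to those in adults". SAP 5.3 says the JAHV pharmacokinetic data "will be provided by age cohort (12 to <18 years, 6 to <12 years, and 2 to <6 years". Protocol 7.2.1 instead expects 4 mg from age 9 and "2-mg for patients < 9 years of age, in order to produce exposures similar to those in adults", and Protocol 7.2 divides the cohorts below 12 as "9 to <12 years, 6 to <9 years, and 2 to <6 years". Protocol 7.4 adds a rule for the extension: "During Part B, as patients age over 9 years old, they will receive baricitinib 4 mg at their next scheduled visit". Protocol Appendix 8 reports that the sponsor "has enrolled the cohort aged 6 to <9 years in the PK cohort in JAHV", and gives the dose for that band as "2 mg (based on predicted data – to be confirmed with observed data". SAP Table JAHW.6.2 tabulates baseline age in four bands with a cut at 9. Both documents say that patients receive the final age-based dose chosen in JAHV.

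**Age-group summaries.** Protocol 10.3.6.1 commits to Part A efficacy and safety summaries at Week 24 for ages 12–17, 6–11 and 2–5 and assigns the details to the SAP. Only the list of contents is worded as optional. The SAP has no subgroup section.

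**Compliance.** SAP 6.8 reports compliance for each treatment period. Expected baricitinib use is the number of days in the period, less interruptions, multiplied by a single daily number of tablets or weight of suspension. A patient who misses less than 20% of expected doses is compliant.

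**The concern.** An SAP issued to follow the amended protocol should carry the same age boundary, particularly as its own baseline table already does. Two analysis consequences matter more than the wording.

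First, a protocol commitment has no specification behind it. Week 24 results by age group could be left out, or produced with contents chosen after the data are seen. Growth is relevant here: Protocol 8.2 lists adverse growth trends, judged for an individual or for an age group, among the possible reasons for discontinuation, yet no growth display by age group is specified.

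Second, Protocol 7.4 doubles the nominal dose of some children during Part B, and the SAP 6.8 formula cannot represent that for suspension. A fully adherent child can be counted noncompliant, or real missed doses can be hidden.

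**Working it through.** The plan states no figure of its own on this point, so there is none to reproduce.

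**1. The two age rules, single-year ages 2 to 17**

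| Age | SAP 5.3.1 (expected) | Protocol 7.2.1 (expected) |
|---|---|---|
| 2–5 | 2 mg | 2 mg |
| 6–8 | 4 mg | 2 mg |
| 9–17 | 4 mg | 4 mg |

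They differ at 3 of 16 single-year ages, by a factor of 2. This counts ages, not patients. Under the protocol rule the 6–11 group of Protocol 10.3.6.1 holds both nominal doses; under the SAP rule it holds one.

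**2. Where age appears in the SAP.** It is a baseline characteristic (Table JAHW.6.2), sets reference limits for vital signs (Table JAHW.8.5) and triglycerides (Table JAHW.8.9), and enters the CDC growth standardisation (8.4). Efficacy is summarised by arm (6.1) and safety by treatment group (6.1.3, Table JAHW.8.1). No outcome or safety table is specified by age group.

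**3. Suspension compliance across a dose change.** Inputs: suspension strength 2 mg/mL (Protocol Table JAHW.6), so 2 mg = 1 mL and 4 mg = 2 mL; Part B lasts 260 weeks. Density cancels in the weight ratio.

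- Part B: 260 × 7 = 1820 days; half is 910.
- Full adherence with a change from 2 mg to 4 mg halfway: 910 × 1 + 910 × 2 = 2730 mL used.
- Expected at 2 mL/day throughout: 1820 × 2 = 3640 mL, so 2730/3640 = 75%, below the 80% line.
- Expected at 1 mL/day throughout: 1820 mL, so 2730/1820 = 150%.

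In general, let *p* be the fraction of the period before the change. With the higher amount, compliance at full adherence is [p × 1 + (1 − p) × 2]/2 = 1 − p/2, which is below 80% when p > 0.4. With the lower amount it is 2 − p. At p = 0.5, a child who takes a fraction *f* of doses evenly then scores 1.5f, which exceeds 80% once f > 0.8/1.5 = 0.533. Such a child could miss nearly 47% of doses and still count as compliant.

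**4. Can the case arise under the protocol?** A child who reaches 9 halfway through Part B does so (168 + 910)/365.25 = 2.95 years after baseline, so is about 6.05 at entry. The whole study is 284 × 7/365.25 = 5.44 years, so this child finishes at about 11.49. Protocol 7.2 offers suspension from 6 to under 12, so the child may use it throughout. The delay to the next scheduled visit is ignored.

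**5. Weight of one child.** In a group of 20, one misclassified child moves the compliant proportion by 1/20 = 5 points. The Part B denominator is not given; if it is smaller, the step is larger.

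**6. Precision of the age-group summaries.** Group sizes are not given. Assuming 3 to 9 patients per group with two-thirds responding, exact 95% intervals are 9%–99% for 2/3, 22%–96% for 4/6 and 30%–93% for 6/9.

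**The case against.** The strongest reply is that the dose conflict has no operational effect. The SAP does not prescribe treatment, and both documents defer to JAHV. That stands: a reader might infer that children aged 6 to 8 will be dosed wrongly, and the documents do not support it.

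A reader might also infer that one baricitinib safety column is an SAP failure that leaves the data monitoring committee unable to see dose. Protocol 10.3.7 does let the committee recommend "discontinuation of a particular dose regimen or discontinuation of the entire study", and Protocol Table JAHW.6 lists the doses under a treatment-group heading. But Protocol 10.3.4 itself specifies safety summaries for baricitinib and adalimumab, and Protocol 10.3.1 specifies efficacy by arm. The committee recommends; it does not itself stop a regimen. Its charter and analysis plan are not among the documents and may already hold a split by dose.

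Growth is better served than a mean plotted over exposure time would suggest. SAP 8.4 standardises by age and sex, gives z-scores and percentiles, and plans spaghetti plots. Protocol 10.3.6.1 does not name growth among the possible contents, so including it is a reasoned addition and not a missed commitment.

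On compliance, one could claim 50% for a child aged 7 in Part A by setting the SAP 5.3.1 dose against 2 mg actually dispensed (168/336 mL). That requires a programmer to ignore the dispensed dose, and SAP 6.8 does not refer to 5.3.1. The Part B result is different: the formula provides one daily amount for a period in which the protocol changes the dose. A careful programmer might split the period unprompted, but the SAP does not say so.

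**Conclusion.** Three limited points hold.

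- SAP 5.3 and 5.3.1 contradict Protocol 7.2, 7.2.1, 7.4 and Appendix 8, and sit badly with the SAP's own baseline bands. Taken alone this is a documentation conflict, and no view is taken on which boundary is right.
- The age-group efficacy and safety details that Protocol 10.3.6.1 assigns to the SAP are absent from it.
- The SAP 6.8 formula misstates suspension compliance when the dose changes within a period: 75% or 150% at full adherence for a change halfway through Part B. This assumes one daily amount is applied to the whole of Part B and that the child stays on suspension. Tablet counts are unaffected if each dose is one tablet.

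The number of children affected is not given and could be zero. A child aged from 9 − 5.44 = 3.56 to under 9 at baseline who completes Week 284 reaches 9 on study, but that is a range of ages and not a share of patients. The primary Bayesian analysis and the success decision are unaffected, because they count baricitinib responders without regard to dose or age. Compound-level safety standards were not supplied and might hold further displays.

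**What to change.** 1. Reconcile SAP 5.3 and 5.3.1 with Protocol 7.2, 7.2.1, 7.4 and Appendix 8.
2. Specify in the SAP the Week 24 efficacy and safety summaries by the three age groups of Protocol 10.3.6.1. Include growth, because Protocol 8.2 allows growth trends to be judged by age group.
3. In SAP 6.8, calculate expected suspension use as the sum, over the days of the period, of the amount prescribed on each day, leaving out days of interruption.
4. Optionally, show baricitinib safety counts and patient-years by dose received, or state that the committee's analysis plan holds them.

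The cost is SAP text and descriptive programming on age, dispensing and exposure data already collected. Cells will be small, so the age-group and by-dose displays should stay at counts and simple descriptive figures, with no comparison between ages or doses.

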6.1. General Considerations

This plan describes *a priori* statistical analyses for efficacy, health outcomes, and safety that will be performed.

Statistical analysis of this study will be the responsibility of Eli Lilly and Company (Lilly). The statistical analyses will be performed using SAS® Version 9.4 or a more recent version.

Not all displays described in this SAP will necessarily be included in the clinical study report (CSR). Not all displays will necessarily be created as a “static” display. Some may be incorporated into interactive display tools instead of or in addition to a static display. Any display described in this SAP and not included in the CSR would be available upon request.

Bayesian analysis will be used as the primary analysis method for the primary endpoint and interim analysis. The posterior probability will be reported and the conclusion will be made based on the prespecified success criteria. The primary endpoint is the proportion of patients with response at Week 24. Response is defined as a 2-step decrease in the level of inflammation (anterior chamber cells) or decrease to 0 in the eye most severely affected at baseline, measured by the SUN criteria (Jabs et al. 2005). **CCI**

Unless otherwise specified, for the endpoints that may relate to both eyes, such as patients with uveitis affecting both eyes, the summary of the data for a given endpoint measure will be based on both affected eyes. The summary statistics may be grouped into “less severely affected eye” and “more severely affected eye” or “right eye” and “left eye” subgroups. The “less severely affected eye” and “more severely affected eye” are defined by the baseline SUN grade for each patient with a higher SUN grade indicating more severity.

Efficacy and health outcomes endpoints will also be summarized using descriptive statistics for the baricitinib arm and adalimumab arm. No treatment comparison will be conducted.

Continuous data will be summarized in terms of the mean, standard deviation (SD), minimum, maximum, and median. Categorical data will be summarized as frequency counts and percentages.

All safety data will be descriptively summarized.

6.1.1. Analysis Populations

For purposes of analysis, the following populations are defined as shown in [Table JAHW.6.1](#).

Table JAHW.6.1. Treatment Period Populations

Population	Description
Modified Intent-to-Treat population	The mITT population is defined as patients who take at least 1 dose of investigational product in part A.
As-observed population	The as-observed population is defined as the patients who complete the analysis visit as scheduled in part B.
Safety population	The safety population is defined as all patients who receive at least 1 dose of investigational product and who do not discontinue from the study for the reason 'Lost to Follow-up' at the first postbaseline visit.

Abbreviation: mITT = modified intent to treat.

Unless otherwise specified, the efficacy and health outcomes analyses will be conducted on the modified intent-to-treat (mITT) analysis set in Part A. For the efficacy and health outcomes analyses in Part B, the analyses will be conducted on as-observed data. Safety analyses will be carried out on the safety population.

In the rare situation where a patient is lost to follow-up at the first postbaseline visit but some safety data exist (e.g., unscheduled laboratory assessments) after the first dose of study drug, a listing of the data or a patient profile will be provided.

6.1.2. Definition of Baseline and Postbaseline Measures

Baseline

The baseline for change from baseline endpoints will be the baseline of Treatment Period Part A (visit at which the patient receives the first dose of investigational product).

Postbaseline

[figure not shown]
Postbaseline measurements are collected after the study drug administration.

6.1.3. Analysis Methods

The primary analysis is to evaluate efficacy of baricitinib in patients with active JIA-U or chronic ANA-positive uveitis. The primary efficacy endpoint is the proportion of responders at Week 24. Response is defined according to the SUN criteria as a 2-step decrease in the level of inflammation (anterior chamber cells) or decrease to 0 in the eye most severely affected at baseline.

Bayesian posterior probability analysis will be used as the primary analysis for Study JAHW Part A. Bayesian analyses will be conducted both at interim and the end of Study JAHW (if the study is not stopped earlier).

Two interim analyses will be performed to potentially stop Study JAHW early due to futility when 10 and 20 patients have completed 24 weeks of treatment, respectively. **CCI**

CCI

Given the proposed overall sample size and timing of interim analyses, the above Bayesian decision rules can be translated to correspond to the following:

- At the first interim analysis, Study JAHW will be stopped if 2 or fewer of the 10 patients are responders.
- If Study JAHW continues, at the second interim analysis, the study will be stopped if 6 or fewer of the 20 patients are responders.

All safety data will be descriptively summarized by treatment groups and analyzed using the safety population. Vital signs, body weight, and other safety variables, including laboratory variables, will be summarized by treatment groups.

Efficacy and health outcomes endpoints will be presented per [Table JAHW.7.1](#) and [Table JAHW.7.3](#).

